16.5 Test Article Accountability, Reconciliation, and Return

The investigator is accountable for all test article supplied by the Sponsor. The designated copies of the completed dispensing and inventory record will be returned to the Sponsor after the Sponsor has performed accountability procedures.

All test articles must be returned to the Sponsor or contract distribution center with the appropriate form. Unused test article may also be destroyed and documented at the investigative site in accordance with GCP and site SOPs.

16.6 Test Article Compliance

Test article should be administered at each scheduled clinic visit. At each clinic visit, patients will be questioned about their compliance with study drug administration.

17.0 MEASURES TO MINIMIZE/AVOID BIAS

Patients are numbered sequentially. Each patient will be assigned a unique number and will keep this number for the duration of the study. Patient numbers will not be reassigned or reused for any reason. Patients should be identified to the Sponsor only by their assigned number, initials, date of birth, and sex. The investigator must maintain a patient master log.

18.0 SAFETY EVALUATION

Routine safety and tolerability will be evaluated from the results of reported signs and symptoms, scheduled physical examinations, vital sign measurements, 12-lead ECGs (including QTc intervals), and clinical laboratory test results.

Safety data will be reviewed by the investigator and the medical monitor. Safety of pexidartinib will be established after 28 days of dosing at the previous dosage group before the next higher dose is initiated.

More frequent safety evaluations may be performed if clinically indicated or at the discretion of the investigator. All AEs will be recorded from the time the patient receives the first dose of study drug until the patient's End of Study visit.

18.1 Physical Examination

Physical examinations will be performed by a licensed physician, physician's assistant, or nurse practitioner.

18.2 Vital Signs

Vital signs will be measured at the study days and times as noted in the flow charts.

18.3 Electrocardiograms

12-lead ECGs will be recorded at screening to assess study eligibility. Please refer to the flow charts for study days and times. For the dose escalation cohorts only, triplicate ECGs will be obtained. Patients should rest in the supine position for at least 5 minutes before the ECG recording is started. The ECGs should be reviewed promptly by a qualified physician (or physician's assistant, nurse practitioner) and any clinically important finding recorded on the appropriate CRF. The investigator is responsible for providing the interpretation of all ECGs. The results will include heart rate, PR interval, QRS interval, QT interval, and QTc interval.

18.4 Safety Laboratory Determinations

Laboratory evaluations will be performed at each participating site at the study visits as noted in the flow charts. For the dose escalation cohorts, blood for CBC values should be obtained mid-cycle after Cycle 1. Please see [Attachment 1](#) for the specific laboratory tests to be performed.

19.0 BIOMARKER SAMPLES

Plasma and spot urine samples will be obtained as noted in the study flow charts.

Details on the preparation, handling, and shipping of blood samples are covered in the Laboratory Manual.

20.0 PHARMACOKINETIC EVALUATION

20.1 Blood Collection

Venous blood samples will be collected in lithium heparin to measure concentrations of pexidartinib for each PK blood collection.

For QD dosing in the dose escalation cohorts, PK samples will be obtained on C1D1 and C1D15 within 30 minutes before dose administration (predose, time 0) and at 30 minutes, 1, 2, 4, and 8 hours post-dosing. For BID dosing, PK samples will be obtained on C1D1 and C1D15 predose (AM) and 1, 2, 4, and 7 hours postdose. The second dose will be administered, and a PK sample will be obtained 1 hour post the second dose (8 hours post the first dose). Predose samples will be obtained on C1D2, C1D8, and C1D16, and then every 4 weeks during continued dosing. Patients should be informed to refrain from taking study drug until they arrive in the clinic. If a patient experiences a DLT or SAE, a single blood sample for PK analysis should be obtained within 48 hours of the event. Samples will be collected and processed according to the instructions in [Attachment 2](#) and [Attachment 3](#).

In the Extension cohorts, PK samples should be obtained pre-dose on C1D1. On C1D15, the samples should be obtained pre-dose and 1, 2, 4, and 6 hours postdose. During continued dosing, PK samples should be obtained once every 4 weeks (predose). PK sampling will no longer occur beyond C40.

Blood samples for PK analysis should be collected at the requested time but the following sample collection windows will be allowed: ± 5 minutes for the 30-minute postdose sample; ± 10 minutes for the hour 1 through 4–8 postdose samples; within ± 30 minutes of dosing on C1D2, C1D8, and C1D16. The exact time of collection should be noted in the CRFs.

If a patient has an afternoon clinic visit, the patient should be instructed to take his or her AM and PM dose as usual. When the patient arrives at the clinic, the PK blood sample should be obtained even though it will be drawn after the patient's AM dose. The time of the AM dose should be entered on the PK CRF, and a comment should be added to the comment field of the CRF to indicate that the PK sample was collected after the AM dose.

Biological specimen samples for pharmacokinetic analysis must be identified with labels provided by the Sponsor.

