13.2 Run-In Period (Selected Cohorts) – Cycle 1 Day(-7), Day(-6), and Day(-4)

1. All 3 days: Recording of concomitant medications and adverse events.

2. All 3 days: Vital signs (sitting blood pressure, pulse rate, and respiratory rate and oral temperature [°F]).
3. All 3 days: Pre-dose blood sample collection for PK analysis and response biomarkers.
4. C1D(-7): Post-dosing blood collection for PK analysis.

13.3 Pre-Treatment (Baseline): Cycle 1 Day 1

Patients will return to the clinic on C1D1 and will undergo the following procedures:

1. Recording of concomitant medications.
2. Vital signs (sitting blood pressure, pulse rate, and respiratory rate and oral temperature [°F]).
3. Standard 12-lead ECG in triplicate 2 minutes apart.
4. Pre-dose blood sample collection for PK analysis and response biomarkers.
5. Pre-dose morning urine collection for response biomarkers.

13.4 Post-Treatment: Cycle 1 Day 1 and Cycle 1 and Day 2

On C1D1, each patient will receive the assigned dose of test article. AE monitoring will be continuous. Vital signs, ECGs, laboratory evaluations, and PK sample collections will be completed at designated times during the study (see [Trial Flow Charts](#)). The blood sample for PK analysis should be collected at the scheduled time, within the windows noted in the PK section. ECG in triplicate will be repeated at 2, 4, and 6 hours after administration of study drug. Pulse and blood pressure will be repeated at 1 and 4 hours post administration of study drug on C1D1. Patients will return to the clinic on the morning of C1D2 prior to dosing on that day for evaluation and blood draw to obtain the predose PK time-point (approximately 12 hours after the previous evening dose for a BID dosing regimen).

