13.5 Cycle 1 Day 8 ± 1 Day

Patients will return for evaluation of AEs, concomitant meds, vital signs, physical exam, clinical laboratory values, and collection of serum and morning urine for biomarker assessments. A predose blood sample for PK and as well as predose blood samples for response biomarkers will be obtained, as well as a predose morning urine for response biomarkers (see [Trial Flow Charts](#), pp. 16–20).

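### In the dose-escalation cohorts, PK samples defined as predose on C1D2, C1D8 and C1D16 may be drawn up to 30 minutes after the dose

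*Combined protocol and SAP*

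**What the plan says.** Section 20.1 defines three single samples in the dose-escalation cohorts: "Predose samples will be obtained on C1D2, C1D8, and C1D16, and then every 4 weeks during continued dosing". Later in the same section, the collection window for those days is within plus or minus 30 "minutes of dosing on C1D2, C1D8, and C1D16".

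For once-daily dosing on C1D1 and C1D15, the section is one-sided before the dose and treats half an hour afterwards as a separate postdose time: "within 30 minutes before dose administration (predose, time 0) and at 30 minutes, 1, 2, 4, and 8 hours post-dosing". That 30-minute sample has its own window of ±5 minutes.

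The procedures sections put the draw before the dose. Section 13.4, for C1D2: "Patients will return to the clinic on the morning of C1D2 prior to dosing on that day for evaluation and blood draw". Section 13.5, for C1D8: "A predose blood sample for PK and as well as predose blood samples for response biomarkers will be obtained". Section 13.6 gives C1D16 the same order as C1D2. The Synopsis and footnote 6 of the escalation flow charts agree.

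On recording, Section 20.1 asks for the exact collection time. Section 16.1 asks for the time of administration on C1D1 and C1D15. For afternoon visits, Section 20.1 accepts a sample drawn after the morning dose, with the dose time and a comment entered on the PK CRF.

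**The concern.** A site or data manager who checks times against the stated window would pass a draw 25 minutes after the dose as a valid predose sample. The same section would class a sample at that time on C1D1 as the 30-minute postdose sample. If absorption has begun, the value is the remaining drug plus a contribution from the new dose.

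Two uses are exposed. First, in once-daily cohorts the C1D1 and C1D15 profiles stop at 8 hours, so C1D2 and C1D16 supply the only point near 24 hours. The Synopsis lists AUC to the last quantifiable time, AUC to infinity, half-life and Kel, and these depend heavily on that point if it is included. Second, any predose or accumulation summary that uses the three days would mix pre- and post-dose values. No rule says how a post-dose sample is to be handled.

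**Working it through.** **Text comparison**

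| Item | Source | Position relative to the dose |
|---|---|---|
| C1D2, C1D8, C1D16: sample type | 20.1, 13.4–13.6, Synopsis, flow-chart footnote 6 | before |
| C1D2, C1D8, C1D16: window | 20.1 | 30 min before to 30 min after |
| C1D1, C1D15 (QD): predose window | 20.1 | 0 to 30 min before |
| 30-minute sample (QD) | 20.1 | after, ±5 min |

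The second row contradicts the first. No stated window applies to the four-weekly predose samples or to the Extension predose samples, so the two-sided rule is confined to these three days.

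**Illustrative size**

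The plan gives no figure to reproduce, and no human absorption rate, lag or half-life. Section 6.3 has animal data only: absorption within 2–3 h and half-life 2–5 h. All inputs here are therefore assumptions: one compartment, tmax 2 or 3 h, half-life 5, 12 or 24 h, doses every 12 or 24 h. The BID model spaces doses evenly, whereas on C1D1 the second dose follows the 7-hour draw, so its C1D2 values are approximate.

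For a unit dose with lag L, concentration is C(t) = ka/(ka − ke) × [exp(−ke(t − L)) − exp(−ka(t − L))], with ke = ln 2 / half-life and ka solved to give the assumed tmax. Doses are summed. The ratio is the value 30 minutes after the new dose divided by the value just before it.

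| Absorption lag | Day | BID | QD |
|---|---|---|---|
| 0 h | C1D2 | 1.37–2.67 | 1.91–11.87 |
| 0 h | C1D8, C1D16 | 1.18–2.61 | 1.45–11.47 |
| 0.25 h | C1D8, C1D16 | 1.11–2.08 | 1.28–8.2 |
| 0.5 h | all three | 0.93–0.99 | 0.93–0.99 |

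A 3 h half-life with no lag stretches the upper ends to about 4.8 (BID) and 68 (QD), because the trough is then near zero.

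**Effect on a once-daily C1D1 profile: one worked case**

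Take half-life 12 h, tmax 2 h, no lag: ke = 0.0578, ka = 1.769.

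- True 24 h value: 0.258. Value at 24.5 h with the second dose taken at 24 h: 0.251 + 0.577 = 0.828. Ratio 0.828 / 0.258 = 3.21.
- Trapezoidal AUC from 0 to 8 h: 5.99. Last segment, correct: (0.651 + 0.258)/2 × 16 = 7.27, total 13.26. Last segment, late: (0.651 + 0.828)/2 × 16.5 = 12.20, total 18.19. Increase: 18.19/13.26 − 1 = 37%.
- Terminal slope from 4, 8 and 24.5 h: the values are 0.820, 0.651 and 0.828. The fitted log slope is positive, so no half-life can be estimated.

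Across the assumed half-lives and tmax values with lag 0–0.25 h, AUC to the last sample rises by 16–48%. A true 12 h half-life is estimated at 31 h or more, or not at all. These cases use the actual collection time, so analysing by actual time does not cure the problem.

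**Accumulation**

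With no lag, the true C1D16/C1D2 ratios are 1.04–2.00. If both samples are drawn 30 minutes late, they become 1.01–1.72 (BID) and 1.00–1.52 (QD), nearer 1 in all 12 scenarios. If only C1D2 is late the ratio falls further; if only C1D16 is late it rises.

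**The case against.** The strongest reply is that the schedule already requires the draw before the dose and that patients are instructed accordingly: "Patients should be informed to refrain from taking study drug until they arrive in the clinic". A post-dose draw would meet the window but breach the schedule. The intent is indeed clear. However, holding the dose until arrival is not holding it until the draw, and the window is the criterion against which a recorded time would be checked. One could also read the tolerance as running around the usual dosing hour with the dose still held. The text does not say so, and one-sided wording would remove the doubt.

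A second reply is that exact collection times make late samples identifiable. This stands only in part. Collection time must be compared with dose time, and Section 16.1 expressly requires dose time only on C1D1 and C1D15. The afternoon-visit rule suggests that the PK CRF can hold a dose time, but no section requires it for these three days.

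Three stronger readings are tempting and are not supported:

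- **That these samples drive escalation.** Section 16.4 rests escalation on DLTs and Grade 2 or greater toxicity. PK informs the move to BID and, if no DLT is seen, the recommended dose, but no trough or accumulation threshold is given.
- **That troughs and accumulation ratios are biased upward.** Trough concentration is not a listed PK parameter in the Synopsis or Section 24.3, which look for accumulation through Cmax and AUC. The C1D16/C1D2 ratio can move either way.
- **That a fixed inflation factor applies.** With a 0.5 h lag the late value is slightly below the trough.

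Nor do the documents say that a post-dose draw will be analysed as a trough. They do not say how it will be handled.

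**Conclusion.** The inconsistency is real and minor: a two-sided window on samples that the plan defines as predose, confined to three days in the dose-escalation cohorts. It matters chiefly for once-daily profiles, where one post-dose draw can spoil the last point behind AUC, half-life and Kel. That rests on the C1D2 and C1D16 values being joined to the preceding day's profile. The Synopsis pairs the days for sampling, but the PK analysis section does not spell this out.

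The size cannot be derived from the documents. The multipliers and the 16–48% AUC effect hold only under the assumed model with absorption starting within 0.25 h; at a lag of 0.5 h the inflation disappears. The number of samples affected is unknown.

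**What to change.** 1. In Section 20.1, change the window for C1D2, C1D8 and C1D16 to within 30 minutes before that day's dose.
2. Confirm that dose time is recorded on those days, and require it if it is not.
3. In the PK analysis, exclude any sample drawn after that day's dose from predose summaries and from the terminal-slope and AUC calculation of the preceding profile. Handle afternoon-visit samples the same way; that rule is a more direct route by which a post-dose sample enters a predose time point.

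The cost is a few words and a filter on recorded times, plus one CRF field if dose time is not already captured. No visit or sample is added. Because the protocol already names an RP2D, many escalation samples have probably been drawn, so the analysis rule in step 3 is the part most likely to change results.

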- ⁴ Visit only conducted for subjects that don't enroll in the phase 4 continuation study or transition immediately to commercial pexidartinib. For patients who miss the 30-day or 12-week post-treatment follow-up MRI, post-treatment radiographic assessments from any source (e.g., primary care provider) within 24 weeks of the last dose are acceptable.
- ⁵ If there is a Grade 2 or higher ALT or AST elevation (i.e., $>3 \times$ ULN) at any time during treatment, the patient should be followed closely (see [Section 14.7](#) for monitoring details).
- ⁶ On C1D1, obtain predose. On C1D15, obtain predose (AM) and 1, 2, 4 and 6 hours postdose. During continued dosing, obtain once every 4 weeks (predose). For patients with afternoon clinic visits, see [Section 20.1](#).
- ⁷ For women of child-bearing potential.
- ⁸ Patients enrolled after the implementation of Amendment 8 will complete these two patient reported outcome (PRO) instruments predose at the clinic on C1D1, C1D15, C2D1, and monthly thereafter, and every 12 weeks after C40, while continuing study drug administration, and at the End of Study visit.
- ⁹ For patients enrolled after the implementation of Amendment 8, six (6) questionnaires will be dispensed at the indicated clinic visits with instructions and reminders to complete the questionnaire on an outpatient basis for 6 consecutive days (Day -6 to Day -1) prior to each monthly clinic visit on C1D1, C2D1, C3D1, etc. (or at every 12- or 24-week visit after C40) while continuing study drug administration. The patient should return the completed questionnaires to site staff at each of the subsequent monthly clinic visits on C1D1, C2D1, C3D1, etc.
- ¹⁰ Morning urine NTX and CTX-II and the following serum markers: IL-6, CSF-1. CD14+/CD16+ monocytes predose (AM) on C1D1 only.
- ¹¹ This assessment will occur every 8 weeks during continued dosing, and every 24 weeks after C40, and (for subjects that don't enroll in the phase 4 continuation study or transition to commercial pexidartinib) approximately 30 days and 12 weeks after the last dose of study drug; additional detail regarding MRI is included in footnote 2. For PVNS patients, the Sponsor will receive radiologic images for possible retrospective analysis of treatment response, to be performed by a central vendor.
- ¹² Monitored throughout the study via safety assessments, observation, and participant reporting.

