14.4 Cycle 1 Day 15 (\pm 2 days)

At the C1D15 visit, AEs, concomitant meds, vital signs, physical exam, test article compliance, and clinical laboratory values will be recorded. An ECG will be obtained, and PK blood samples

will be obtained predose (AM) and at 1, 2, 4 and 6 hours postdose (for patients who have an afternoon clinic visit, the documentation of dosing and PK sampling times is described in [Section 20.1](#)). If obtained at the pre-dose Baseline, a repeat tumor biopsy and/or FDG-PET scan may be obtained.

For patients enrolled after the implementation of Amendment 8, give the patient the NRS for PVNS Symptoms questionnaire to complete predose. Then give the patient the WOMAC questionnaire to complete predose. Then dispense six (6) NRS for PVNS Symptoms questionnaires with instructions and reminders to complete the daily questionnaire on an outpatient basis for the 6 consecutive days (Day -6 to Day -1) prior to the C2D1 study visit and to bring the completed questionnaires back at that visit.

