16.0 TEST ARTICLE

16.1 Test Article Administration

Test article (study drug) will be administered only to patients who have signed and dated an informed consent form. Test article will be administered on days 1 through 28 or longer in the fasting state with 240 mL (8 oz.) of room-temperature water. The patient should fast at least 2 hours before administration and 1 hour after administration of the test article. Patients will be permitted to eat a low-fat snack (e.g., crackers, toast, tea) during the fasting period if needed. Test article will be taken orally by swallowing the capsules. For patients with tumors of the head and neck area who may have difficulty swallowing capsules, test article may be administered by emptying the contents of the dose (e.g., 3 x 200 mg capsules in the morning, and 2 x 200 mg capsules in the evening for a total daily dose of 1000 mg/day) into an empty glass.

Approximately 6 ounces of orange juice, apple juice, or cola should be added to the glass, stirred vigorously with a spoon and the patient should drink the contents, add 2 additional ounces to the glass, stir again and drink the remaining contents. The entire dose should be consumed within 30 minutes and the capsule shells should be discarded in a bio-disposable hazard bag provided by the site. NOTE: The Plexxikon Medical Monitor must be consulted prior to implementation of this alternative method of test article administration.

Test article administration will start on C1D1 and should be taken once daily for the initial cohort. Subsequent cohorts may utilize a twice daily dosing regimen, with study drug being administered at approximately 12-hour intervals. On PK collection C1D1 and C1D15, the patients will be administered pexidartinib capsules at the clinical site. The time of the administration will be recorded. On non-PK collection days, patients will administer the study drug at home. Missed doses (i.e., outside of a + 2-hour window) should be skipped and not administered as a double dose at the next administration. Patients who vomit their dose should be instructed to NOT to make up that dose. Patients should take precautions to prevent accidental ingestion of or exposure to investigational drug by family members or other cohabitants.

Food-Effect Assessment:

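### The afternoon-visit PK rule in Section 20.1 is carried over to C1D15, where it conflicts with the five-sample series and on-site dosing and costs each affected Extension patient the only routine PK profile

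*Combined protocol and SAP*

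**What the plan says.** **Sampling schedule.** For the Extension cohorts, Section 20.1 asks for one predose sample on C1D1, five samples on C1D15 (predose, 1, 2, 4 and 6 h), and one predose sample every 4 weeks up to C40. Section 14.4 repeats the C1D15 series, with a visit window of ±2 days. The Food-Effect text in Section 16.1 repeats it again and keeps C1D15 as a fasted PK visit.

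**Link to the afternoon rule.** In the sentence that sets the C1D15 series, Section 14.4 adds: "for patients who have an afternoon clinic visit, the documentation of dosing and PK sampling times is described in" Section 20.1. Footnote 6 of the Extension flow chart lists the C1D1, C1D15 and 4-weekly samples and then says: "For patients with afternoon clinic visits, see" Section 20.1.

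**The afternoon rule.** For any afternoon visit, Section 20.1 says "the patient should be instructed to take his or her AM and PM dose as usual". On arrival, "the PK blood sample should be obtained even though it will be drawn after the" morning dose. On recording, "The time of the AM dose should be entered on the PK CRF", with a comment "to indicate that the PK sample was collected after the AM dose". The exact collection time of every PK sample is also recorded.

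**Dosing on visit days.** Section 16.1 says: "On PK collection C1D1 and C1D15, the patients will be administered pexidartinib capsules at the clinical site". Section 16.6 says drug should be administered at each scheduled clinic visit.

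**Analysis.** Section 24.3 plans a noncompartmental analysis (Cmax, tmax, AUC, clearance, volume, half-life) and correlates Cmax and AUC with SAEs. It has no rule for samples taken off schedule.

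**The concern.** The afternoon paragraph describes one draw after a dose taken before arrival. That can work for a single monthly sample, but not for a visit whose purpose is a profile from predose to 6 h. Because Section 14.4 and footnote 6 direct C1D15 to the paragraph without exception, a site can follow the protocol and still fail to collect the series the protocol requires.

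For such a patient there is no other routine profile: C1D1 and the 4-weekly visits give single predose samples. The only other multi-sample PK is the optional food-effect subset (predose, 2 h and 4 h, fasted and then fed), which covers only patients who consent to it and stops at 4 h. The disease-specific cohorts have about 10 patients, so each missing profile is about one tenth of a cohort's serial PK.

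A lesser issue arises at the 4-weekly visits, where the same rule puts a post-dose concentration in a slot labelled predose.

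**Working it through.** The plan states no figure on this point, so there is none to reproduce. The check has three parts.

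**1. C1D15 instructions side by side (Extension cohorts)**

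| Item | C1D15 text | Afternoon paragraph, Section 20.1 |
|---|---|---|
| Morning dose | Given at the clinical site (16.1) | Taken as usual, before arrival |
| Predose sample | Required (14.4, 20.1, 16.1 Food-Effect) | Not possible; the draw follows the dose |
| Number of samples | Five | One, in the singular |
| Exception for C1D15 | – | None |

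A site cannot satisfy both columns.

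**2. What can still be collected at C1D15.** The documents give no clock times. Assume a home dose at 07:00, 08:00 or 09:00 and arrival on the hour from 12:00 to 16:00, which gives 3 × 5 = 15 combinations. Time after dose is arrival minus dose time:

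| Dose | Hours after dose at arrival (12:00 to 16:00) |
|---|---|
| 07:00 | 5, 6, 7, 8, 9 |
| 08:00 | 4, 5, 6, 7, 8 |
| 09:00 | 3, 4, 5, 6, 7 |

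- Predose, 1 h and 2 h samples: unobtainable in 15 of 15, since the earliest draw is at 3 h.
- Single arrival draw coinciding with a scheduled time (4 h or 6 h): 5 of 15.
- If the patient stayed on, which the paragraph does not ask: both the 4 h and 6 h samples in 3 of 15, the 6 h sample only in 6, and neither in 6.

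One draw, or at best the 4 h and 6 h points, does not give a noncompartmental Cmax, tmax or AUC over the dosing interval.

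**3. Size of the mislabelling at 4-weekly visits.** Assumptions: one compartment, first-order absorption, steady state, equal doses every 12 h, single-dose tmax 2.5 h, and a draw 4 to 8 h after the dose. The documents give no human tmax or half-life. Section 6.3 has animal values only (absorption within 2 to 3 h, half-lives 2 to 5 h). Half-life is therefore varied over 5, 12 and 24 h.

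With ke = ln 2 / half-life and ka solving ln(ka/ke)/(ka − ke) = 2.5,

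C(t) ∝ e^(−ke·t)/(1 − e^(−12ke)) − e^(−ka·t)/(1 − e^(−12ka)).

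Example at half-life 5 h: ke = 0.1386, ka = 0.876.

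- t = 4 h: 0.5743/0.8105 − 0.0301 = 0.6785.
- t = 12 h (trough): 0.1895/0.8105 − 0.0000 = 0.2337 (carrying unrounded terms).
- Ratio: 0.6785/0.2337 = 2.90.

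| Half-life | ke | ka | C(4 h)/trough | C(8 h)/trough |
|---|---|---|---|---|
| 5 h | 0.1386 | 0.876 | 2.90 | 1.74 |
| 12 h | 0.0578 | 1.305 | 1.58 | 1.26 |
| 24 h | 0.0289 | 1.646 | 1.26 | 1.12 |

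So a post-dose value is about 1.1 to 2.9 times trough over this range. A half-life shorter than 5 h would give larger ratios.

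**The case against.** **The cross-reference may concern recording only.** Section 14.4 points to Section 20.1 for how dosing and sampling times are documented, and the singular wording of the afternoon paragraph fits a monthly draw better than a series. All the text specific to C1D15 keeps the full series or on-site dosing. This is a fair reading, but it does not remove the problem. What the site finds in Section 20.1 is an instruction on dosing and drawing, with no C1D15 exception, and footnote 6 refers to it without mentioning documentation.

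**The Extension cohorts' PK profile is not lost as a whole.** A reader might infer that it is. The documents do not support that: morning C1D15 patients keep all five samples, nothing indicates how many visits fall in the afternoon, and the optional food-effect subset supplies some further multi-sample data. The loss is per affected patient.

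**The trough data are not corrupted without trace.** A reader might infer that too. Section 20.1 requires the morning dose time, the collection time and a CRF comment, so these samples can be found and placed at their true time after dose. Section 24.3 specifies no trough summary or trough-over-time analysis. The synopsis, in text about dose escalation, limits the PK analysis to the first 28 days. This objection stands and makes the monthly point secondary. It does not help C1D15, since a flag cannot recover samples never drawn.

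**PK is a primary objective only for dose escalation** (Section 8.1), and exposure-response work is exploratory. This limits the consequence. It also means that exclusion of an affected patient from every exposure-response analysis is not established; only the profile parameters from that visit are lost.

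**The ratios rest on assumed human PK.** This is correct. Section 6.3 suggests human clearance may be slow, which favours the lower ratios. Whether an afternoon draw is past the peak is likewise an inference from animal data.

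**Conclusion.** The contradiction is in the text and should be corrected. As written, Section 14.4 and footnote 6 apply a one-draw rule after a home dose to a visit that elsewhere requires five samples starting predose and drug given on site.

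For each patient handled under the rule, the predose, 1 h and 2 h samples are lost under every clock time assumed, and Cmax, tmax and AUC cannot be derived from C1D15. How many patients this affects cannot be determined from the documents; it could be none. Neither a cohort-wide loss of PK nor a failure of a planned trough analysis follows from the text.

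The 4-weekly mislabelling is secondary. Its size of about 1.1- to 2.9-fold depends wholly on the assumed half-life (24 to 5 h), tmax and draw time, and the values concerned can be identified.

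**What to change.** 1. **Section 20.1:** limit the afternoon paragraph to the single-sample visits from C2D1 onward.
2. **Section 14.4 and Extension flow-chart footnote 6:** remove the reference to that paragraph for C1D15, and state that C1D15 is to be scheduled, within its existing ±2 days, so that the predose-to-6 h series can be collected.
3. **Sections 14.4, 16.1, 16.6, 20.1 and footnote 6:** reconcile these on where and when drug is taken on PK visit days. Section 16.6 needs attention even after step 1, because a home dose before an afternoon visit from C2D1 onward still sits uneasily with it.
4. **Section 24.3:** add one sentence saying that, if predose or trough values are summarised, samples flagged as post-dose are left out of those summaries and used only at actual time after dose.

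The cost is wording in four sections and one footnote. No new samples or CRF fields are needed. The downside is less appointment flexibility for one visit.
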